### **1.6.2 Immune Biomarker**

Like many other cancers, HCC cells develop multiple strategies of escaping tumor-specific immunity such as the accumulation of myeloid-derived suppressor cells (MDSC), suppression of tumor-associated antigen-reactive lymphocytes by T regulatory cells (Treg) and dysfunctional dendritic cells. MDSCs will be quantified by flow using a panel of markers that we have already standardized HLA DR-, CD 14-, CD11b +,CD33+. These mechanisms that drive HCC progression makes the development of efficacious immunotherapies for HCC very challenging.

The hypothesis of this study is based on the following rationale: c-Kit is one of the targets of tivozanib and functions as a receptor for stem cell factor (SCF), a well-studied tumor-derived factor expressed by various human and murine tumor cell lines. In mouse tumor models, abrogation of tumor-expressed SCF by RNA interference has been shown to significantly reduce MDSC expansion and restore the effector function of tumor-infiltrating T cells. Furthermore, blockade of c-Kit by immunotherapeutic treatment with an anti-c-Kit monoclonal antibody prevented the development of Tregs, tumor-specific T cell anergy and tumor angiogenesis. In view of this role of c-Kit, we hypothesize that modulation of c-Kit signaling via tivozanib may have a novel role in reversing tumor-induced immune suppression. In RPCI studies, levels of

ERK2 phosphorylation will be compared between c-Kit+ and c-Kit immune cells to allow us to address the role of c-Kit expression on immune cells as the mechanism by which tivozanib modulates the immunosuppressive network in advanced stage HCC patients. Results will be correlated to outcome measurements on patients (progressed, median survival time).

Targeting of c-Kit to prevent MDSC and Treg accumulation in murine tumor models has been successfully demonstrated with sunitinib. Importantly, in our studies with HCC patients we have shown that multifocal immunosuppressive networks are present at high levels in patients compared to healthy controls and that they are reduced following sorafenib treatment (provided in Preliminary Data). Specifically, the frequency of MDSCs and Tregs decreased in advanced stage HCC patients following their treatment with sorafenib.

The downstream signaling effect of receptor tyrosine kinase (RTK) inhibitors, such as tivozanib, is modulation of mitogen-activated protein (MAP) kinase phosphorylation. Although RTKs converge on several MAP kinases, this study will examine tivozanib-mediated modulation of ERK2 phosphorylation by high-throughput multi-parameter flow cytometry. In addition, this study will measure the extent of intracellular ERK2 phosphorylation as this adaptor signaling molecule plays a critical role in the function of immunosuppressive and effector immune cells. The expression level of c-Kit and level of ERK2 phosphorylation will be examined in circulating MDSC and Tregs analyzed from patients with advanced, inoperable hepatocellular carcinoma receiving tivozanib as part of a Phase 2 study. One prediction is that ERK2 phosphorylation will decrease in c-Kit+ MDSC and Tregs upon treatment with tivozanib. Diminished c-Kit signaling will therefore coincide with a reduction in the frequency of MDSC and Tregs relative to effector anti-tumor T cells.

### **1.7 Risks and/or Benefits**

The known adverse events from tivozanib include diarrhea, fatigue, asthenia, hypothyroidism, dysphonia, hypertension, palmo-plantar erythrodysesthesia, and alopecia. Refer to **Table 1** and the current Tivozanib Investigator Brochure.

## **2 RATIONALE**

HCC is a common malignancy worldwide and rising in incidence in the United States. Most patients have incurable/advanced disease at presentation. The subset of Child Pugh Class A and early Class B liver dysfunction patients have been shown to benefit from sorafenib which is considered the ‘standard of care’; as it improved overall survival and PFS when compared with placebo in well conducted large randomized Phase 3 trials despite a lack of radiographic response. The time to symptom improvement endpoint, however, was not met and median survival still remains less than 11 months. Targeting angiogenesis is now the backbone of HCC therapy, but better agents and biomarkers that define subsets of patients who are likely to derive the most benefit from such therapies are still needed. Tivozanib is an oral potent inhibitor of VEGFR-1, VEGFR-2, and VEGFR-3 and represents a tolerable and effective treatment for VEGF driven malignancies based on data from 12 completed trials in cancer patients. It showed safety and efficacy in renal cell cancer and is being evaluated in combination with sorafenib in Phase 3 studies in RCC. Given that HCC is a highly vascular VEGF driven malignancy and like

RCC, is a malignancy where sorafenib has proven efficacy, we hypothesize tivozanib may have meaningful clinical benefit. Although HCC pathogenesis is driven by many factors, of the identified angiogenic factors, VEGF is the most potent and specific and has been identified as a crucial regulator of both normal and pathologic angiogenesis. *In vivo* data suggest that VEGF inhibition with tivozanib has therapeutic potential in HCC. Elevated VEGF levels correlate with advanced stage and poor prognosis in HCC. The preclinical efficacy of tivozanib in HCC models, the tolerability in early clinical trials and success of a targeting angiogenesis in HCC form the rationale for our hypothesis that tivozanib may be tolerable and improve PFS in HCC patients beyond 24 weeks, the expected median PFS for patients receiving sorafenib. *In vitro*, sorafenib has been reported to have anti-HCV effects and in recently completed human studies we have seen significant differences in survival using baseline immune cell numbers. It is expected that some effects of novel multi-targeted TKIs maybe immune mediated and hence propose to test this hypothesis prospectively using validated assays already in place.

### **3 OBJECTIVES**

#### **3.1 Primary Objective**

The primary endpoint of the study is PFS at 24 weeks in patients with advanced HCC. Patients who remain alive without evidence of disease progression (per RECIST) for at least 24 weeks after enrollment will be considered PFS responders.

#### **3.3 Study Design**

This is a multicenter Phase 1b/2 study of tivozanib in patients with advanced inoperable hepatocellular carcinoma.

##### **3.3.1 Phase 1b**

Based on monotherapy tolerability data of tivozanib from 14 studies an oral dose of 1.5 mg daily has been recommended for Phase 2 testing. Since tivozanib has not been tested in HCC patients, and HCC patients who are candidates for systemic therapies tend to have Child Pugh Class A or early B cirrhosis, this study will start with a Phase 1 dose escalation study.

The Phase 1b portion of the study follows a modified 3 + 3 design. Typical 3 + 3 studies start at the lowest dose. This modified design starts at patients at the middle dose. The first 3 patients will be treated with a 1 mg oral once daily dose. Depending on observed toxicity rates, the dose may be deescalated to 0.5 mg, or escalated to 1.5 mg. The standard 3 + 3 dose (de)escalation rules will be followed, as specified in the table below. Dose level will be considered, tolerable following completion of 1st cycle of treatment. The dose of 1 mg daily, was found to be the tolerated dose in the phase 1b portion and will be the phase 2 dose.

Number of Patients with DLT at a Given Dose Level	Escalation Decision rule
0 out of 3	Enter 3 patients at the next higher dose level.
$\geq 2$ out of 3	Stop dose escalation and declare this dose level as the maximally administered dose (highest dose administered). Enroll 3 additional patients at the next lowest dose level if only 3 patients were treated previously at that dose.
1 out of 3	Enter 3 more patients at this dose level. If 0 of these 3 patients experience DLT, proceed to the next dose level. If $\geq 1$ of this group suffer DLT, then stop dose escalation, and declare this dose as the maximally administered dose. Enroll 3 additional patients at the next lowest dose level if only 3 patients were treated previously at that dose.
$\leq 1$ out of 6 at the highest dose level below the maximally administered dose	This is generally the recommended Phase 2 dose. At least 6 patients must be entered at the recommended Phase 2 dose

### 3.3.2 Phase 2

The Phase 2 portion is a two-stage, single arm, unblinded trial allowing for early termination in case of futility. The 6 Phase 1b patients treated at the recommended Phase 2 dose will be included in the Phase 2 trial. Details are provided in **Section 11**.

### 3.3.3 Treatment Cycle

A cycle will be defined as 28 days. At the full dose, this will be 21 days on treatment with 7 days off. However, in the case of a dose reduction patients will be treated starting on day 1 of the cycle, every other day for 10 doses. Treatment will continue until progression or toxicity. Response/ progression will be assessed Q 8 weeks or q 2 months by CT scan. (MRI when patients have contraindication to CT). Steady state PK will be assessed at Day 15, as this is the first study in patients with liver dysfunction.

### 3.4 Target Accrual and Study Duration

Between 6 and 18 patients will be enrolled in the Phase 1b portion of this study. Six Phase 1b patients treated at the recommended Phase 2 dose will be included in the Phase 2 portion of this study. An additional 31 patients will be enrolled for the Phase 2 portion, for a total Phase 2 sample size of 37. This study is expected to accrue 9 patients to the Phase 1b, for a combined

sample of size of 40 (9+37-6). If 18 patients are enrolled in the Phase 1b, the maximum combined sample size will be 49 (18+37-6).

Accrual is expected to take up to 4 years. The duration the patient will be on study will be approximately 2 years.

## 4 SUBJECT SELECTION

### 4.1 Inclusion Criteria

To be included in this study, subjects must meet the following criteria:

1. Advanced staged HCC (unresectable and not amenable to local or regional therapy; or metastatic HCC). The diagnosis of HCC should be based on at least one of the following:
  - MRI or CT consistent with liver cirrhosis AND at least one solid liver lesion measuring  $\geq 2$  cm, with characteristics arterial enhancement and venous washout regardless of AFP levels.
  - AFP  $\geq 400$  ng/mL AND evidence of at least one solid liver lesion  $\geq 2$  cm regardless of specific imaging characteristics on CT or MRI.
  - Histological/cytology biopsy confirming HCC.
2. Patients must have measurable disease per RECIST 1.1 criteria defined as at least one lesion that can be accurately measured in at least one dimension, and that has not been the target of local or regional therapy including transarterial chemoembolization, intra-arterial chemotherapy, ethanol or radiofrequency ablation.
3. Age  $\geq 18$  years.
4. Life expectancy of greater than 3 months.
5. Patients must have organ and marrow function as defined below:
  - Child-Pugh liver function Class A. (Appendix G)
  - AST  $\leq 5$  x Institutional upper limits of normal (ULN)
  - Total bilirubin  $\leq 3$  mg/dL
  - INR  $\leq 2.0$  (unless due to therapeutic warfarin use)
  - Serum albumin  $> 2.8$  g/dL
  - Creatinine  $\leq 1.5$  x Institutional ULN
  - ANC  $\geq 1200/\text{mm}^3$
  - Platelets  $\geq 60,000/\text{mm}^3$
  - Hgb  $\geq 8.5$  g/dL

NOTE: The lower absolute neutrophil count (ANC) and platelet cut-offs are designed to accommodate the large number of patients with HCC who have portal hypertension and splenic

sequestration. Given the adverse profile of tivozanib these reduced cut-offs are thought to be safe.

6. Patients must not have any evidence of bleeding diathesis or active gastrointestinal bleeding.
7. Patients must not be known to be HIV positive; drug-drug interaction with study medication and HIV medications is not well characterized and could lead to unwanted side effects.
8. Patients must not have other uncontrolled intercurrent illnesses (excluding HBV or HCV). This includes (but is not limited to) ongoing or active infection, symptomatic congestive heart failure, unstable angina pectoris, cardiac arrhythmia, or psychiatric illness/social situations that would limit compliance with study requirements.
9. Sexually active fertile patients (male and female), and their partners, must agree to use medically accepted methods of contraception during the course of the study and for 3 months after the last dose of the study drug.
10. Female patients of childbearing potential must have a negative pregnancy test at screening.
11. Have an ECOG Performance Status of  $\leq 2$ . Refer to **Appendix B**.
12. Subject or legal representative must understand the investigational nature of this study and sign an Independent Ethics Committee/Institutional Review Board approved written informed consent form prior to receiving any study related procedure.

#### **4.2 Exclusion Criteria**

Subjects will be excluded from this study for the following:

1. Patients who have had prior anti-angiogenic therapy, including but not limited to sorafenib, brivanib, bevacizumab, or sunitinib.
2. Patients who have had any prior line of systemic therapy including cytotoxic agents or molecularly targeted agents for advanced/unresectable disease. Any number of prior regional therapies with transarterial chemoembolization (TACE), brachytherapy with Yttrium-90 microsphere, intra-arterial chemotherapy, surgery, or ablative therapy is allowed.
3. Prior liver transplantation and on immunosuppression; drug-drug interaction with study medication and immunosuppression is not well characterized and could lead to unwanted side effects.
4. Known symptomatic or uncontrolled brain metastases or epidural disease.
5. Patient has a corrected QT interval (QTcF)  $> 500$  ms at screening.
6. The patient is unable to swallow pills or diagnosed with a gastrointestinal disorder that are likely to interfere with the absorption of the study drug or with the patient's ability to take regular oral medication.
7. The patient is pregnant or breastfeeding.
8. Patients with second primary cancer (except adequately treated nonmelanoma skin cancer, curatively treated in-situ carcinoma of the cervix or superficial bladder cancer, or other solid

tumors including lymphoma without bone marrow involvement curatively treated with no evidence of disease for  $\geq 5$  years).

9. The patient has a previously identified allergy or hypersensitivity to components of the study treatment formulation.
10. Patients receiving any medications or substances that are strong inducers of CYP3A4 are ineligible. Moderate and mild inducers of CYP3A4 should be used with caution, as they may reduce the efficacy of Tivozanib.
11. Urine protein: creatinine ratio  $> 1$  see (Appendix- H)

### **4.3 Inclusion of Women and Minorities**

Both men and women and members of all races and ethnic groups are eligible for this study.

## **5 INVESTIGATIONAL PRODUCT**

### **5.1 Active Substance and Source**

Tivozanib is formulated for oral administration as a white opaque number 4 gelatin capsule. Tivozanib 1 mg, capsules will be used in this study.

### **5.2 Drug Shipment**

Tivozanib, manufactured by AVEO/Astellas Pharmaceuticals, will be shipped to the participating site from the drug depot.

Drug shipment records will be retained by the investigational pharmacist or designee.

### **5.3 Storage and Stability**

The Investigator or designate is responsible to store and dispense the investigational product and will be responsible for ensuring that study drug is securely maintained in a locked, limited-access facility, in accordance with the applicable regulatory requirements.

Tivozanib is to be stored at room temperature ( $15^{\circ}\text{C} - 25^{\circ}\text{C}$ ), in a dry place, and in a secure location.

Tivozanib bottle labels will bear the appropriate label text for investigational agents, as required by governing regulatory agencies.

Complete study drug information (including packaging, labeling, storage and disposition) is provided in the Tivozanib Investigator's Brochure (IB).

### **5.4 Handling and Disposal**

The Investigator or designee will be responsible for dispensing and accounting for all investigational drug, exercising accepted medical and pharmaceutical practices. Study drugs must be handled as cytotoxic agents and appropriate precautions taken per the institution's

environmentally safe handling procedures. All investigational drugs will be dispensed in accordance with the Investigator's prescription or written order.

All products dispensed will be recorded on a product accountability record. Records of product lot numbers and dates received will be entered on a product accountability form. This record will be reviewed by the Sponsor's staff or representative during periodic monitoring visits. It is the Investigator's responsibility to ensure that an accurate record of investigational drug issued and returned is maintained.

Under no circumstances will the Investigator supply investigational drug to a third party or allow the investigational drug to be used in a manner other than as directed by this protocol.

## **6 TREATMENT PLAN**

### **6.1 Preparation and Administration**

[figure not shown]
Treatment will be administered in an outpatient basis. Reported adverse events (AEs) and potential risks are described in **Section 9**. Appropriate dose modifications are described in **Section 0**. No other investigational or commercial drugs or therapies other than that described below may be administered with the intent to treat the subject.

The amount of tivozanib dispensed to the subject at the beginning of each dosing cycle will be sufficient to allow for 3 weeks (21 days) of consecutive once-daily dosing of tivozanib. Only 21 capsules will be dispensed per cycle. In the case of a dose reduction patient will be given 10 capsules for every other day dosing for 10 doses.

Tivozanib capsules will be dispensed for oral use only and taken daily for 21 days and off for 7 days. The intended dose is 1 mg daily on Day 1 through Day 21 and no drug on Day 22 through Day 28, in a 28-day cycle. Patients start Cycle 2 after Day 28 and repeat dosing from Day 1 to Day 21. In the case of dose reduction patients will be intended to take 1 mg every other day starting on Day 1. After 10 doses (every other day) patients will have no drug through the end of the 28-day cycle. Patients will start the next cycle after Day 28 of the previous cycle.

The prescribed daily dose of tivozanib hydrochloride is to be taken, once per day (or every other day in the case of a dose reduction), preferably in the morning, with water, and with or without food. Only one capsule of tivozanib hydrochloride should be taken each dose. If a dose is vomited or otherwise missed that day for any reason, the dose for that day should not be made up. The next dose should be taken as prescribed at the next scheduled time (i.e., one capsule is to be taken even if the previous dose was vomited or otherwise missed; additional dose(s) should not be taken at any time to make up for any missed dose(s)). Grapefruit and grapefruit juice should be avoided during the study.

In the event that tivozanib hydrochloride dosing is interrupted, the duration of cycle/treatment will not be extended; doses missed during the interruption will be captured as omitted rather than delayed.

**Figure 1. Dosing Schema****Table 2. Dose Schedule**

Level	Dose
-1*	0.5 mg PO daily for 21 days, then 7 days off (q 28 days cycles)
1 (starting dose)	1 mg PO daily for 21 days, then 7 days off (q 28 days cycles)
2	1.5 mg PO daily for 21 days, then 7 days off (q 28 days cycles)

\*0.5 mg not manufactured (Per Amendment #11), please see section 6.2.4

## 6.2 Dose Modifications

### 6.2.1 Definition of Dose-Limiting Toxicity

A DLT is any Grade 3 or higher toxicity that is possible, probable, or definitely related to study drug.

Management and dose modifications associated with the above AEs are outlined in the below sections. Dose level will be, considered tolerable following completion of 1st cycle of treatment.

Patients who experience a DLT will be dose reduced to the next lower dose cohort for continuation on the study.

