**Table 3. Tivozanib Hydrochloride Dose Modification Guidelines for Drug-Related Adverse Events**

Drug-Related Adverse Events (excluding Hypertension  )	Action Taken	Subsequent Dosing Modification
Grade 1	No dose interruption, or reduction required; adverse event management is at the discretion of the Investigator	None required; Dosing may continue at the same dose
Grade 2	No dose interruption, or reduction required; adverse event management is at the discretion of the Investigator	None required; Dosing may continue at the same dose
Grade 3	Interrupt dosing until toxicity resolves to grade $\leq 1$	Dosing may resume at reduced dose (see below for dose reduction guidelines)
Grade 4	Interrupt dosing until toxicity resolves to grade $\leq 1$ .	Dosing may resume at reduced dose (see below for dose reduction guidelines).

1 Hypertension must be treated as described in Section 6.2.5 prior to any dose modification

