### 6.2.4 Tivozanib Hydrochloride Dose Reduction

Dose reductions of tivozanib by 0.5 mg/day will be required for patients with  $\geq$  Grade 3 drug-related adverse events. This excludes grade  $\geq 3$  hypertension, nausea, vomiting, and diarrhea, without adequate supportive care. Hypertension, nausea, vomiting, and diarrhea may resume at the same dose level after adequate supportive care, in the investigators opinion it is safe to proceed at the same dose level. If hypertension, diarrhea, nausea, and vomiting recurs despite adequate supportive care tivozanib must be dose reduced, up to 2 dose reductions are allowed. Once a patient's dose of tivozanib is reduced, it may not be re-escalated through the

remainder of the patient's participation in the study. 1 mg capsules every other day for 10 doses will be used, as 0.5 mg capsules are no longer manufactured. According to the drug manufacturer AVEO Pharmaceuticals, this dosing regimen will achieve comparable exposure to 0.5 mg QD, based on the half-life of Tivozanib.

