### 6.2.5 Management of Hypertension

Hypertension (HTN) that occurs during study treatment must be treated with anti-hypertensive drugs prior to any dose reduction. Recommended management of HTN for subjects receiving study drug is presented in **Appendix C** and **Appendix D**.

Persistent HTN is defined as 2 consecutive elevated blood pressure (BP) measurements preferably taken in the clinic and obtained at least 1 hour apart. It is recommended that 24-48 hours should elapse between the decision steps. For a listing of recommended DHP (dihydropyridine) calcium channel blockers, angiotensin converting enzyme (ACE) inhibitors, and angiotensin receptor blockers, see **Appendix D**, Recommended Anti-hypertensive Medications. **Note:** If a subject has controlled HTN on an anti-hypertensive regimen at baseline and then develops a worsening of HTN requiring more intensive therapy than the previous regimen, this would be considered Grade 3 HTN.

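### A related Grade 3 hypertension, nausea, vomiting or diarrhea event requires a dose reduction under 6.2.1 but may resume at the same dose under 6.2.4

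*Combined protocol and SAP*

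**What the plan says.** Section 6.2.1 defines the event class: "A DLT is any Grade 3 or higher toxicity that is possible, probable, or definitely related to study drug". It refers the reader onward ("Management and dose modifications associated with the above AEs are outlined in the below sections") and closes with the dosing consequence: "Patients who experience a DLT will be dose reduced to the next lower dose cohort for continuation on the study". Neither the definition nor the consequence has an exempt event type.

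Section 6.2.4 requires a 0.5 mg/day reduction for drug-related events of Grade 3 or higher, but leaves out Grade 3 or higher "hypertension, nausea, vomiting, and diarrhea, without adequate supportive care". For these it says: "Hypertension, nausea, vomiting, and diarrhea may resume at the same dose level after adequate supportive care", subject to the investigator's opinion that this is safe. If the event recurs despite adequate supportive care, reduction becomes mandatory. A reduced dose may not be raised again.

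Section 6.2.5 requires antihypertensive drugs before any dose reduction. It also fixes a grade by rule: for a patient whose hypertension was controlled on medication at baseline, worsening "requiring more intensive therapy than the previous regimen, this would be considered Grade 3 HTN".

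Table 3, which 6.2.2 introduces as suggested criteria, sets aside hypertension only. Its Grade 3 row says: "Dosing may resume at reduced dose (see below for dose reduction guidelines", followed by the closing bracket. Section 6.2.3 likewise names hypertension as its only exception.

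**The concern.** Both sections use mandatory language and overlap on the same patients. An investigator who treats a related Grade 3 diarrhea, sees it settle, and restarts at the same dose complies with 6.2.4 and breaches 6.2.1. One who reduces complies with 6.2.1 and withholds an option that 6.2.4 grants.

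The choice lasts. The bar on re-escalation sits in 6.2.4, not in 6.2.1, but it applies to any reduction once made. In a multicenter trial, the dose a patient receives for the rest of treatment could then depend on which section a site happens to follow. Deviation logs and monitoring also have no single rule to check against.

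**Working it through.** The plan states no figure on this point, so there is none to reproduce. The check is a comparison of passages plus one piece of dose arithmetic.

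**Scope.** I compare Grade 3 events only, because section 6.4 has its own discontinuation rule for non-hematologic Grade 4 events.

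**Step 1: one event under each section.** Take a related Grade 3 nausea, vomiting or diarrhea event, first occurrence, without adequate supportive care beforehand.

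- 6.2.1: it is a DLT, and the patient is to be reduced. No condition is attached.
- 6.2.4: it is outside the required reduction, and the same dose may be resumed after supportive care if judged safe.
- 6.2.3: dosing is interrupted until Grade 1 or lower, and may then resume one level lower at the investigator's discretion.
- Table 3: interruption, then dosing may resume at a reduced dose, with a pointer to the reduction guidelines that follow.

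6.2.1 and 6.2.4 cannot both govern this event.

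**Step 2: hypertension.** Take a patient with controlled hypertension at baseline whose regimen has to be intensified on study.

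- 6.2.5: the event is Grade 3 by rule, and antihypertensive treatment must precede any reduction.
- 6.2.1: if at least possibly related, it is a DLT and the patient is to be reduced.
- 6.2.4: after adequate supportive care, the same dose may be resumed.

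Taken alone, 6.2.5 could be satisfied by treating first and reducing afterwards. The conflict comes from 6.2.4, which says that reduction need not follow.

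**Step 3: where the sections agree.** If the event recurs despite adequate supportive care, 6.2.4 also requires reduction. The conflict is confined to events that 6.2.4 exempts.

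**Step 4: size of the dose difference.** Inputs from section 6.1: full dose is 1 mg daily on Days 1 to 21; the reduced regimen is 1 mg every other day for 10 doses.

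- Full dose per cycle: 21 × 1 mg = 21 mg.
- Reduced dose per cycle: 10 × 1 mg = 10 mg.
- Difference: (21 − 10)/21 = 11/21 = 0.524, or 52% less per cycle.

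**Step 5: how often.** This cannot be computed. Table 1 gives hypertension 40.9%, diarrhea 18.2%, nausea 8.8% and vomiting 5.3%, but these are all-grade rates pooled from renal cell carcinoma studies. They show only that the event types are familiar with this drug.

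**The case against.** **6.2.1 points to the later sections, so the specific rule governs.** That is a sensible way to read the protocol and probably close to the intent. But the pointer gives the later sections no precedence, and the unconditional reduction sentence comes after it. The contradiction may be a drafting gap, but it remains in the text.

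**The reduction sentence is for Phase 1b only.** Its reference to a lower cohort is dose-finding language, and tolerability is tied to the first cycle. This reading is plausible, but the text does not state it. Section 6.2.4 is not limited by phase either, so the conflict would remain within Phase 1b.

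**Same-dose resumption is a matter of investigator judgment.** This stands: some variation between sites would persist under 6.2.4 alone. It does not explain why 6.2.1 removes the same judgment.

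Three stronger readings are tempting, and the documents do not support them.

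- *Table 3 as a separate contradiction.* The table says that dosing may resume at a reduced dose, refers to the guidelines below it, and is described in 6.2.2 as suggested. Its wording needs aligning, but it is not an independent conflict.
- *These events drove the choice of 1 mg.* Section 11.1 expected Dose Level 2, while 3.3.1 reports: "The dose of 1 mg daily, was found to be the tolerated dose in the phase 1b portion and will be the phase 2 dose". The four event types count as DLTs under the written definition, but no document lists the DLTs that occurred. A broad DLT definition for cohort decisions can also coexist with a more flexible rule for individual dosing.
- *The 24-week PFS result becomes uninterpretable.* Section 11.6 includes all enrolled patients, so the primary result describes a starting dose with modifications during treatment. The two-stage decision rule does not depend on this point.

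**Conclusion.** The contradiction is real and follows from the text alone. For a related Grade 3 hypertension, nausea, vomiting or diarrhea event without adequate supportive care, 6.2.1 makes reduction mandatory and 6.2.4 permits resumption at the same dose. Where the two paths diverge for a patient at the 1 mg daily dose, the planned amount is 10 mg against 21 mg per cycle, with no return to the higher amount.

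That size rests on the regimens in 6.1 and on the no-re-escalation rule in 6.2.4. How many patients are affected is unknown. For Phase 2 patients, the conclusion also assumes that the 6.2.1 reduction sentence applies to them, which the text neither states nor excludes. No view is taken here on which dosing rule is right. The text should be corrected; the point does not undermine the trial's statistical design.

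**What to change.** Amend 6.2.1, 6.2.4 and 6.2.5 so that Grade 3 hypertension, nausea, vomiting and diarrhea have one stated dosing consequence, and align the wording of Table 3 and 6.2.3 with it. State whether the 6.2.1 reduction sentence applies to Phase 1b, Phase 2 or both. The sponsor decides the rule.

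The cost is amendment wording and notice to the sites. No visit, sample or change in sample size is needed.

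Optionally, the report could list the Phase 1b DLTs by event type and dose level, so that readers can see the basis for the chosen dose. The correction does not depend on that listing.
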